	2	4 (28.6%)	0	4 (20.0%)
	1	2 (14.3%)	0	2 (10.0%)
GASTROINTESTINAL DISORDERS				
- Overall -	any	13 (92.9%)	6 (100.0%)	19 (95.0%)
	3	2 (14.3%)	0	2 (10.0%)
	2	4 (28.6%)	1 (16.7%)	5 (25.0%)
	1	7 (50.0%)	5 (83.3%)	12 (60.0%)
DIARRHOEA	any	10 (71.4%)	4 (66.7%)	14 (70.0%)
	3	1 (7.1%)	0	1 (5.0%)
	2	4 (28.6%)	0	4 (20.0%)
	1	5 (35.7%)	4 (66.7%)	9 (45.0%)
VOMITING	any	9 (64.3%)	3 (50.0%)	12 (60.0%)
	2	1 (7.1%)	1 (16.7%)	2 (10.0%)
	1	8 (57.1%)	2 (33.3%)	10 (50.0%)
NAUSEA	any	7 (50.0%)	4 (66.7%)	11 (55.0%)
	2	1 (7.1%)	1 (16.7%)	2 (10.0%)
	1	6 (42.9%)	3 (50.0%)	9 (45.0%)
DRY MOUTH	any	2 (14.3%)	1 (16.7%)	3 (15.0%)
	1	2 (14.3%)	1 (16.7%)	3 (15.0%)
RETCHING	any	2 (14.3%)	1 (16.7%)	3 (15.0%)
	1	2 (14.3%)	1 (16.7%)	3 (15.0%)
CONSTIPATION	any	1 (7.1%)	1 (16.7%)	2 (10.0%)
	1	1 (7.1%)	1 (16.7%)	2 (10.0%)
DYSPEPSIA	any	1 (7.1%)	1 (16.7%)	2 (10.0%)
	1	1 (7.1%)	1 (16.7%)	2 (10.0%)
ABDOMINAL PAIN	any	1 (7.1%)	0	1 (5.0%)
	1	1 (7.1%)	0	1 (5.0%)

ID: AE022SP Listing of Patients with Dose Modification or Interruption Due to Adverse Events during Remission Induction Phase and Overall	STREAM Template: AEL02 Analysis Population: Safety Evaluable Population Variables Displayed: Add a new column to AEL02 for “The start date of AE leading to dose modification/interruption”. Numeric Precision and Formatting of Statistics: See mockup.
---	---

ID: AE023SP Non-Serious Adverse Events Reported in \geq 5% of Patients	STREAM Template: EUDRAT01 Analysis Population: Safety Evaluable Population Analysis Variables: This table will be used to fulfill EudraCT and clintrials.gov disclosure requirements. It summarizes, for each treatment group, the number of patients, and the number of events, for non-serious AEs occurring in \geq 5% of patients. Results will be displayed by SOC and PT within each SOC. Number of events at the SOC level is not displayed. Statistics and Calculation Methods: Percentages are based on N in column heading. For each preferred term, multiple occurrences of the same AE in an individual are counted only once for the number of patients, and counted separately for the number of events. Sort by: Display the data alphabetically by SOC, and by PT alphabetically within a SOC . Numeric Precision and Formatting of Statistics: See mockup.
--	---

MedDRA System Organ Class MedDRA Preferred Term	rituximab (N=98)	
	Patients	Events
Total number of patients with at least one non-serious adverse event occurring at relative frequency \geq 5% and number of events	95	1742
Blood And Lymphatic System Disorders		
Anaemia	21	34
Leukopenia	10	17
Neutropenia	32	58
Thrombocytopenia	11	22
Eye Disorders		
Lacrimation Increased	9	9
Vision Blurred	5	5
Gastrointestinal Disorders		
Abdominal Pain	17	27
Abdominal Pain Upper	9	13
Diarrhoea	54	123
Dyspepsia	14	16
...		

NOTE: Number of events includes all occurrences.

ID: AE023.2SE
 
Serious Adverse Events, Fatal SAEs and SAEs Related to Study Medication
	
STREAM Template: EUDRAT02
 
Analysis Population: SE Population
 
Analysis Variables: See mockup.
 
This table will be used to fulfill EudraCT disclosure requirements. It summarizes, by treatment group, by SOC and preferred term, the following:
 
 • Number of patients with serious adverse events (SAEs) • Number of SAEs • Number of patients with fatal SAEs • Number of SAEs resulting in death (fatal) • Number of SAEs related to study medication • Number of SAEs related to study medication and resulting in death 
Number of events at the SOC level is not displayed.
 
Statistics and Calculation Methods: Percentages are based on N in column headings. For each preferred term, multiple occurrences of the same AE (that meet the relevant filter) in an individual are counted only once for the number of patients, and counted separately for the number of events.
 
Sort by: Display the data alphabetically by SOC, and by PT alphabetically within a SOC .

---	--

NOTE: Number of events includes all occurrences.

MedDRA System Organ Class MedDRA Preferred Term	Patients (All)	Event s (All)	Patients (Fatal)	Events (Fatal)	Events (Related)	Events (Fatal and Related)
Blood And Lymphatic System Disorders						
Anaemia	nnn	nnn	nnn	nnn	nnn	nnn
Coagulopathy	nnn	nnn	nnn	nnn	nnn	nnn
Febrile Neutropenia	nnn	nnn	nnn	nnn	nnn	nnn
Cardiac Disorders						
Acute Myocardial Infarction	nnn	nnn	nnn	nnn	nnn	nnn
Atrial Fibrillation	nnn	nnn	nnn	nnn	nnn	nnn
...						

NOTE: Number of events includes all occurrences.


ID: AE024SP
 
Common Adverse Events Reported in $\geq 10\%$ of Patients during Remission Induction Phase and Overall
	
STREAM Template: None
 
Analysis Population: Safety Evaluable Population
 
Analysis Variables:
 
Table of AEs grouped by System Organ Class (SOC) and listed by Preferred Term (PT) that occurred at a frequency $\geq 10\%$ for each phase.
 
Note: "with at least one AE " means "with at least one AE which occurred for $\geq 10\%$ of patients".
 
Numeric Precision and Formatting of Statistics: See mockup.

--	---

MedDRA System Organ Class	RITUXIMAB (N=25)
Total number of patients with at least one AE	24 (96.0%)
UPPER RESPIRATORY TRACT INFECTION	11 (44.0%)
HEADACHE	10 (40.0%)
DIARRHOEA	8 (32.0%)
EPISTAXIS	7 (28.0%)
ARTHRALGIA	6 (24.0%)
CHEST PAIN	5 (20.0%)
CONJUNCTIVITIS	5 (20.0%)
COUGH	5 (20.0%)
GRANULOMATOSIS WITH POLYANGIITIS	5 (20.0%)
NAUSEA	5 (20.0%)
PYREXIA	5 (20.0%)
HYPOGAMMAGLOBULINAEMIA	3 (12.0%)
MIGRAINE	3 (12.0%)
NASOPHARYNGITIS	3 (12.0%)
PHARYNGITIS	3 (12.0%)
RHINITIS	3 (12.0%)
TREMOR	3 (12.0%)
URINARY TRACT INFECTION	3 (12.0%)
VIRAL INFECTION	3 (12.0%)
VOMITING	3 (12.0%)

Investigator text for AEs is coded using MedDRA version 20.1.
Percentages are based on N.
Table includes only AEs occurring in $\geq 10\%$ of patients in at least one treatment group.
For frequency counts by preferred term, multiple occurrences of the same AE in an individual are counted only once.

7. SAFETY LABORATORY ANALYSES

7.1 Safety Laboratory Analyses

Safety hematology and serum chemistry laboratory samples are taken during each planned study visit.

Treatment-emergent clinically relevant laboratory test abnormalities are to be reported as adverse events on the Adverse Event eCRF and so will be reported as AEs. This is required for planned samples taken at study visits and also for any unscheduled samples taken.

For hematology and chemistry parameters, following summaries will be produced:

- Descriptive summaries, including changes from baseline, of values at baseline and throughout the study.
- The number of patients with values outside the normal upper and lower limit at each visit.

7.2 Acute-phase Reactants

Samples for measurement of erythrocyte sedimentation rate and C-reactive protein are taken during each study visit for analysis by the site's local laboratory. The parameters values and their changes from baseline will be summarized descriptively by visit and study phase.

7.3 Immunologic and Antibody Assessments

B- and T-cell populations are measured at baseline and each subsequent visit.

Samples for measurement of IgA, IgG, IgM and total immunoglobulins are taken at screening, baseline and then at each visit from Month 1 onwards. These will be summarized descriptively by visit and study phase and as changes from baseline.

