- Treatment with rituximab or other biologic B cell-targeted therapy (e.g., anti-CD19, anti-CD20, anti-CD22, or anti-B-lymphocyte stimulator [BLys]/BAFF) within 6 months prior to baseline visit
- Previous treatment with an anti-alpha 4 integrin antibody or co-stimulation modulator
- Previous treatment with other cell-depleting therapies, including, but not limited to, investigational agents (e.g., alemtuzumab [CAMPATH[®]], anti-CD4, anti-CD5, anti-CD3, and anti-CD11a)
- Receipt of oral or IV CYC within the previous 4 months prior to the baseline visit
- Receipt of infliximab within the previous 3 months prior to the baseline visit

- Receipt of adalimumab within the previous 2 months prior to the baseline visit
- Receipt of etanercept within the previous 1 month prior to the baseline visit
- Treatment with any investigational agent within 28 days of baseline or 5 half-lives of the investigational drug (whichever is longer)
- Receipt of any live or attenuated vaccine within 28 days prior to baseline
 - It is recommended that a patient's vaccination record and the need for immunization should be carefully reviewed and updated prior to receiving rituximab (see Section 4.4.3).
- Intolerance or contraindications to IV glucocorticoids

In case of receipt of any other immunosuppressant therapy (apart from corticosteroids), contact the Sponsor.

Exclusions Related to Laboratory Findings

- Positive serum human chorionic gonadotropin measured at screening or a positive pregnancy test prior to the first rituximab infusion for participants of childbearing potential
- Positive tests for hepatitis B surface antigen (HBsAg), hepatitis B core antibody (HBcAb), hepatitis B virus (HBV), or hepatitis C serology
- Level of IgM below LLN of age-specific reference range
- *Level of IgG below 5.65 mg/ml*
- Absolute neutrophil count (ANC) $< 1.5 \times 10^3/\mu\text{L}$
- Platelet count $< 130 \times 10^3/\mu\text{L}$
- Estimated GFR $< 15 \text{ mL/min/1.73 m}^2$ (calculated using the Schwartz formula; see Appendix 3)
- Alanine aminotransferase (ALT) or aspartate aminotransferase (AST) levels $> 2.5 \times$ the upper limit of normal (ULN) (for age and sex) that cannot be attributed to underlying GPA or MPA

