4.5.3.6 Immunologic Assessments

Determination of B- and T-cell populations will be performed by fluorescence-activated cell sorter (FACS) analysis, including, but not limited to, CD3, CD4, CD8, CD16/56, CD19, CD27, CD4/45RA/45RO, and CD8/45RA/45RO. In addition, quantitative immunoglobulin levels (including total immunoglobulin, immunoglobulin A [IgA], IgG, and IgM isotype levels).

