5.2.3.7 Hypogammaglobulinemia

Decreases in IgA, IgG, and IgM have been observed in adult patients with GPA and MPA following treatment with rituximab. No increased rate in overall infections or serious infections was observed after the development of low IgA, IgG, or IgM levels. Assessment of the Roche safety database and published literature reveals that development of hypogammaglobulinemia after rituximab treatment in pediatric patients with various underlying disease has been observed, and, in some cases, this has been reported as severe and long term requiring long-term IVIg treatment. However, attribution of these events to rituximab is limited by potential alternate etiologies, such as common variable immunodeficiency disease, severity of underlying diseases, use of rituximab as a last resort after exposure to other immunosuppressive agents, and limited clinical data including lack of randomized clinical trials, retrospective data collection, and lack of detailed safety data reporting. Importantly, the majority of these cases were not reported to have been associated with serious infections.

Patients with IgG and IgM levels below the *exclusionary levels per section 4.1.2*, at screening will not be enrolled in the study. The investigator should closely monitor the patient's immunoglobulin levels during the study. *If immunoglobulin levels decrease following rituximab treatment, and require specific medical care or management, repeat dosing can be considered at the discretion of the investigator, based on the assessed benefit/risk.* IVIg (restricted to replacement dosing for hypogammaglobulinemia) may be given at the discretion of the investigator.

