2.1.1 Primary Safety Outcome Measures

The primary safety outcome measures are:

- Frequency, nature, and severity of AEs
- Frequency of laboratory abnormalities

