
ID: LB004SP
 
Laboratory Abnormalities by Visit and Baseline Status
	
STREAM Template: None
 
Analysis Population: Safety Evaluable Population
 
Mock format: See below for specific example with 4 extra columns.
 
Analysis Variables: See LB001SP for parameters to be included and the appropriate analysis visits.
 
Statistics and Calculation Methods: Use the normal ranges given within the data. For each lab test and visit, include the following rows: (a) For Baseline, should have rows for Low, Normal, and High. (Always display all 3, even if count is 0.) (b) For Post-baseline visits, should have rows for Low – Change from Baseline Low – Sustained Low – Baseline Missing Normal High – Change from Baseline High – Sustained High – Baseline Missing
 
For post-baseline visits, only display the “Low – Baseline Missing” and “High – Baseline Missing” rows when they have a non-zero count. For all other rows, always display, even if count is 0.
 
ALB.BASE1, ALB.RANGEB1, ALB.RANGE
 
Analysis visits to include are: Baseline, Weeks 1 to 3, Months 1, 2, 4, 6, 12 and 18.
 
Percentages are based on n.
 
Numeric Precision and Formatting of Statistics: See mockup (although we have just the one treatment group) – noting request above for rows to be presented.

---	---

Key Laboratory Assessments with Values Outside the Normal Limits
Safety-Evaluable Patients

Lab Test	Visit		Placebo (N=66)	Lab 37.5 mg (N=64)	Lab 125 mg (N=62)	Lab 250 mg (N=66)	All Lab (N=192)
Alanine Aminotransferase	Baseline	n	66	64	62	66	192
		Normal	59 (89.4%)	59 (92.2%)	53 (85.5%)	58 (87.9%)	170 (88.5%)
		High	7 (10.6%)	5 (7.8%)	9 (14.5%)	8 (12.1%)	22 (11.5%)
	Week 4	n	60	53	55	60	168
		Normal	55 (91.7%)	51 (96.2%)	51 (92.7%)	55 (91.7%)	157 (93.5%)
		High - Change from Baseline	1 (1.7%)	1 (1.9%)	1 (1.8%)	1 (1.7%)	3 (1.8%)
		High - Sustained	4 (6.7%)	1 (1.9%)	3 (5.5%)	4 (6.7%)	8 (4.8%)
	Week 8	n	52	52	54	50	156
		Normal	48 (92.3%)	50 (96.2%)	50 (92.6%)	43 (86.0%)	143 (91.7%)
		High - Change from Baseline	1 (1.9%)	2 (3.8%)	1 (1.9%)	3 (6.0%)	6 (3.8%)
		High - Sustained	3 (5.8%)	(0.0%)	3 (5.6%)	4 (8.0%)	7 (4.5%)
	Week 12	n	48	44	43	47	134
		Normal	43 (89.6%)	43 (97.7%)	41 (95.3%)	41 (87.2%)	125 (93.3%)
		High - Change from Baseline	1 (2.1%)	1 (2.3%)	(0.0%)	4 (8.5%)	5 (3.7%)
		High - Sustained	4 (8.3%)	(0.0%)	2 (4.7%)	2 (4.3%)	4 (3.0%)
	Week 16	n	43	41	39	42	122
		Normal	38 (88.4%)	40 (97.6%)	39 (100.0%)	35 (83.3%)	114 (93.4%)

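### In the readable SAP no table counts children with low immunoglobulins, although the frequency of laboratory abnormalities is a primary safety outcome, and no rule marks IgG values measured after IVIg

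*SAP*

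**What the plan says.** SAP 2.1.1 lists "Frequency of laboratory abnormalities" as a primary safety outcome. Protocol 4.5.3.6 places total immunoglobulin, IgA, IgG and IgM among the safety assessments. Protocol 5.2.3.7 reports hypogammaglobulinemia in rituximab-treated children, in some cases severe and long term, and asks investigators to monitor levels closely.

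The laboratory outputs are specified as follows.

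- SAP 7.1 opens its list with "For hematology and chemistry parameters, following summaries will be produced". The list includes "The number of patients with values outside the normal upper and lower limit at each visit".
- SAP 7.4, LB004SP (the table of abnormalities by visit and baseline status) says: "See LB001SP for parameters to be included and the appropriate analysis visits". LB001SP names hematology and serum chemistry tests and no immunoglobulin.
- LB005SP, LB006SP and LB007SP are CTCAE shift tables for hematology, chemistry and urinalysis.
- SAP 7.3 covers the immunoglobulins: "These will be summarized descriptively by visit and study phase and as changes from baseline".

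On replacement, Protocol 5.2.3.7 states: "IVIg (restricted to replacement dosing for hypogammaglobulinemia) may be given at the discretion of the investigator". The rules in SAP 3.3 for choosing a value within a visit window look at visit type and closeness to the planned day. They do not mention IVIg.

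**The concern.** A low immunoglobulin level is an expected laboratory abnormality of this drug in this age group, and a primary outcome asks how often laboratory abnormalities occur. Descriptive statistics do not answer that. The normal range depends on age: Protocol 4.1.2 itself excludes on "Level of IgM below LLN of age-specific reference range". A summary pooled over ages 2 to 17 cannot show how many children are below their own limit. The IgG entry limit is an absolute 5.65 mg/mL, so a child already below an age-specific limit may enter. A count therefore has to separate lows present at baseline from lows that develop on study.

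IVIg adds a second, conditional problem. Infused IgG raises measured IgG and total immunoglobulin. Without a flag, a child on replacement looks like a child who has recovered. If immunoglobulins were added to LB004SP with no IVIg rule, that child could be classed as normal.

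**Working it through.** **1. The plan's own figure.** The plan gives no figure for low immunoglobulins. Its one numerical safety statement (SAP 2.2) is a 95% probability of seeing at least one event when the true incidence is 11% or more, with n = 25. Check: 1 − 0.89^25 = 0.946. It reproduces to rounding and does not bear on whether immunoglobulins are counted.

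**2. Which readable outputs would count a low immunoglobulin?**

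| Output | Scope | Counts low immunoglobulin? |
|---|---|---|
| SAP 7.1 out-of-range counts | Hematology, chemistry | No |
| LB004SP by visit and baseline status | LB001SP tests | No |
| LB005SP to LB007SP | Hematology, chemistry, urinalysis | No |
| SAP 7.3 | Immunoglobulins | No, values and changes only |
| LB004.1SP listing | No restriction stated | Possibly listed, but gives no frequency or denominator |
| Adverse event tables | Reported events | Only if recorded as an event |

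**3. Which low values become adverse events?** Protocol 5.3.6 treats a laboratory value as clinically significant if it comes with a symptom, changes study drug, or requires a change in concomitant therapy. Starting IVIg for a low value meets the third condition, so that child should reach the event tables. A low value with no symptom and no treatment meets none of them. The rationale for the version 5 amendment says low IgG often needs no specific management, so this group may not be small. The documents do not give its size.

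**4. Visits.** SAP 7.3 and the schedule of assessments sample immunoglobulins at screening, baseline and every visit from Month 1. LB004SP uses baseline, Weeks 1 to 3 and Months 1, 2, 4, 6, 12 and 18. Extending its test list without its visit list would miss Months 9 and 15 and the visits after Month 18.

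**5. Possible effect of IVIg on mean IgG (assumed inputs).** Let k of 25 children be on IVIg, each raised by d g/L. The shift in the mean is k × d / 25.

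- k = 1, d = 2: 0.08 g/L
- k = 3, d = 4: 0.48 g/L
- k = 5, d = 6: 1.20 g/L
- k = 0: zero

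**6. Effect on a count with no IVIg rule (assumed).** If 5 of 25 would be low and IVIg lifts 3 above the limit, the count falls from 5/25 = 20% to 2/25 = 8%.

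**7. Would dropping post-IVIg values repair the mean?** Assume 22 children at 8 g/L, 3 at 4 g/L without replacement, and a lift of 3 g/L.

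- Without IVIg: (22 × 8 + 3 × 4)/25 = 7.52
- All values kept: (22 × 8 + 3 × 7)/25 = 7.88, an error of +0.36
- The 3 children dropped: 8.00, an error of +0.48

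Here exclusion is worse than keeping the values. That holds whenever the lift is smaller than the gap between these children and the rest.

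**The case against.** The strongest reply is that part of the SAP cannot be read. Section 10 is redacted, and a stray mock-up title for total immunoglobulin under EX007.2SP suggests that another immunoglobulin output was designed. A below-limit count or an IVIg rule may exist there. This stands, and it limits the point to the readable text.

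A reader might infer that the plan understates hypogammaglobulinemia and loses the worst-affected children. The documents do not support that. The count tables omit immunoglobulins; they do not give a figure that is too low. Children who start IVIg for a low value should be recorded as adverse events, and the AE024SP mock-up has a hypogammaglobulinaemia row. CM003.2SP lists medications for other indications, and its mock-up carries start and stop dates, so in a trial of about 25 patients IVIg use can be traced by hand.

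Nor does SAP Section 3 rely on means alone. It also gives the median, minimum and maximum, and change from baseline is within child, which removes much of the objection to pooling ages. The median is less sensitive than the mean to raising a few low values. The minimum shows the lowest child but not how many are low.

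What survives is narrower. Untreated, asymptomatic low values have no readable count, and nothing marks a value taken after IVIg.

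**Conclusion.** The point holds in limited form. In the readable SAP, a primary safety outcome is specified without any count of low IgG, IgM, IgA or total immunoglobulin, although the protocol identifies this risk in children. The uncounted group is children whose low values cause no symptoms and change no treatment; the documents give no basis for its size. It would be wrong to go further and say the means are biased. The IVIg effect depends on use that the documents do not report, applies to IgG and total immunoglobulin only, and is zero if no child is treated. The 0.08 to 1.20 g/L range rests on assumed numbers of children and assumed IgG rises. The conclusion also assumes that the redacted text holds neither the count nor an IVIg rule. The change is worth making before the analysis; the omission does not invalidate the safety analysis.

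**What to change.** Unless Section 10 already provides this:

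- **LB004SP:** add IgG, IgM, IgA and total immunoglobulin at every visit where they are sampled, including Months 9 and 15 and the later follow-up visits. Use age-specific normal ranges and the existing rows by baseline status. Add a row for any post-baseline low value; VS003SP already has such a row for vital signs.
- **IVIg in LB004SP:** count a child on replacement IVIg as low, or in a separate row for children on IVIg, and not as normal.
- **SAP 7.3:** keep all values in the summaries, flag IgG and total immunoglobulin values taken after IVIg, and show the number of children on IVIg at each visit. Do not make exclusion of post-IVIg values the main analysis, since it removes the lowest children and can push the mean further up.

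The cost is SAP wording, some table rows and a little programming. The samples, the normal ranges and the concomitant-medication dates are already collected, so no new data are needed.

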7.4 Laboratory Output Specifications

ID: LB001SP
 
Laboratory Test results and Change from Baseline by Visit
	
STREAM Template: LBT01
 
Analysis Population: Safety Evaluable Population
 
Analysis Variables: Single output file with separate page for each lab parameter as required by the protocol. Create tables for:
 
 Hematology: hematocrit, hemoglobin, red blood cells and indices (mean corpuscular volume, mean cell hemoglobin, mean corpuscular hemoglobin concentration), white blood cells, absolute differential [neutrophils, lymphocytes, monocytes, basophils], and platelet counts Serum chemistry: ALT/SGPT, alkaline phosphatase, AST/SGOT, calcium, chloride, creatinine, glycosylated hemoglobin (HbA_{1c}), phosphate, potassium, sodium, total bilirubin (direct and indirect will be performed if total bilirubin is greater than the ULN), total protein, urea, uric acid 
Sort order for tables: alphabetical by lab test (within hematology and chemistry)
 
Statistics and Calculation Methods: Per standard display.
 
Analysis visits to include are: Baseline, Weeks 1 to 3, Months 1, 2, 4, 6, 12 and 18. Values at visits to include only patients for whom a baseline value is included.
 
Numeric Precision and Formatting of Statistics: See mockup

---	---

Laboratory Test: SGPT/ALT (U/L)

Rituximab
(N=25)

Visit	Value at Visit	Change from Baseline
Baseline		
n	24	
Mean (SD)	25.54 (22.20)	
Median	17.00	
Q1 - Q3 (IQR)	xx.x - xx.x (xx.x)	
Min - Max	7.0 - 79.0	
Week 1		
n	21	20
Mean (SD)	27.43 (21.50)	1.75 (12.47)
Median	17.00	4.00
Q1 - Q3 (IQR)	xx.x - xx.x (xx.x)	xx.x - xx.x (xx.x)
Min - Max	7.0 - 95.0	-34.0 - 19.0
...		


ID: LB004SP
 
Laboratory Abnormalities by Visit and Baseline Status
	
STREAM Template: None
 
Analysis Population: Safety Evaluable Population
 
Mock format: See below for specific example with 4 extra columns.
 
Analysis Variables: See LB001SP for parameters to be included and the appropriate analysis visits.
 
Statistics and Calculation Methods: Use the normal ranges given within the data. For each lab test and visit, include the following rows: (a) For Baseline, should have rows for Low, Normal, and High. (Always display all 3, even if count is 0.) (b) For Post-baseline visits, should have rows for Low – Change from Baseline Low – Sustained Low – Baseline Missing Normal High – Change from Baseline High – Sustained High – Baseline Missing
 
For post-baseline visits, only display the “Low – Baseline Missing” and “High – Baseline Missing” rows when they have a non-zero count. For all other rows, always display, even if count is 0.
 
ALB.BASE1, ALB.RANGEB1, ALB.RANGE
 
Analysis visits to include are: Baseline, Weeks 1 to 3, Months 1, 2, 4, 6, 12 and 18.
 
Percentages are based on n.
 
Numeric Precision and Formatting of Statistics: See mockup (although we have just the one treatment group) – noting request above for rows to be presented.

---	---

Key Laboratory Assessments with Values Outside the Normal Limits
Safety-Evaluable Patients

Lab Test	Visit		Placebo (N=66)	Lab 37.5 mg (N=64)	Lab 125 mg (N=62)	Lab 250 mg (N=66)	All Lab (N=192)
Alanine Aminotransferase	Baseline	n	66	64	62	66	192
		Normal	59 (89.4%)	59 (92.2%)	53 (85.5%)	58 (87.9%)	170 (88.5%)
		High	7 (10.6%)	5 (7.8%)	9 (14.5%)	8 (12.1%)	22 (11.5%)
	Week 4	n	60	53	55	60	168
		Normal	55 (91.7%)	51 (96.2%)	51 (92.7%)	55 (91.7%)	157 (93.5%)
		High - Change from Baseline	1 (1.7%)	1 (1.9%)	1 (1.8%)	1 (1.7%)	3 (1.8%)
		High - Sustained	4 (6.7%)	1 (1.9%)	3 (5.5%)	4 (6.7%)	8 (4.8%)
	Week 8	n	52	52	54	50	156
		Normal	48 (92.3%)	50 (96.2%)	50 (92.6%)	43 (86.0%)	143 (91.7%)
		High - Change from Baseline	1 (1.9%)	2 (3.8%)	1 (1.9%)	3 (6.0%)	6 (3.8%)
		High - Sustained	3 (5.8%)	(0.0%)	3 (5.6%)	4 (8.0%)	7 (4.5%)
	Week 12	n	48	44	43	47	134
		Normal	43 (89.6%)	43 (97.7%)	41 (95.3%)	41 (87.2%)	125 (93.3%)
		High - Change from Baseline	1 (2.1%)	1 (2.3%)	(0.0%)	4 (8.5%)	5 (3.7%)
		High - Sustained	4 (8.3%)	(0.0%)	2 (4.7%)	2 (4.3%)	4 (3.0%)
	Week 16	n	43	41	39	42	122
		Normal	38 (88.4%)	40 (97.6%)	39 (100.0%)	35 (83.3%)	114 (93.4%)
		High - Change from Baseline	2 (4.7%)	1 (2.4%)	(0.0%)	3 (7.1%)	4 (3.3%)
		High - Sustained	3 (7.0%)	(0.0%)	(0.0%)	4 (9.5%)	4 (3.3%)
	Week 20	n	37	36	37	36	109
		Normal	32 (86.5%)	33 (91.7%)	33 (89.2%)	31 (86.1%)	97 (89.0%)
High - Change from Baseline		4 (10.8%)	3 (8.3%)	3 (8.1%)	3 (8.3%)	9 (8.3%)	
	High - Sustained	1 (2.7%)	(0.0%)	1 (2.7%)	2 (5.6%)	3 (2.8%)	

High: >ULN; Low: <LLN.
 Low & Change from Baseline: Normal or high at baseline, but low post-baseline.
 Low & Sustained: Low at baseline, and low post-baseline.
 Normal: Normal at visit.
 High & Change from Baseline: Normal or low at baseline, but high post-baseline.
 High & Sustained: High at baseline, and high post-baseline.

Source: Biostatistics [REDACTED] pgn(/allergy/11r/gb27862/final/programs/t_lab_shift)
 Database (LOCKED) [REDACTED] Datasets (asl alb)
 : Generated 09JAN14 07:40 Page 1 of 66

ID: LB005SP
 
Laboratory Test Shift Table: Highest NCI CTCAE Grade Post-Baseline: [High / Low] Hematology
	
STREAM Template: LBT14
 
Analysis Population: Safety Evaluable Population
 
Mock format: See mockup below.
 
Analysis Variables: See LB001SP for parameters to be included and the appropriate analysis visits.
 
Include patients with a missing baseline value.
 
Statistics and Calculation Methods: Use CTCAE grades, as appropriate. Use all available post-baseline data, not just windowed (analysis visit) results.
 
Percentages are based on n.
 
Numeric Precision and Formatting of Statistics: See mockup (although we have just the one treatment group) – noting request above for rows to be presented.
 
Additional Outputs:
 
A similar output will be provided for the following safety lab categories:
 
  
 ID	Lab Category	
   
 LB006SP	Chemistry	
 
 LB007SP	Urinalysis	
  
	ID	Lab Category	LB006SP	Chemistry	LB007SP	Urinalysis
ID	Lab Category						
LB006SP	Chemistry						
LB007SP	Urinalysis						

[figure not shown]
Absolute neutrophil count

Post-baseline NCI-CTCAE Grade	Baseline NCI-CTCAE Grade	Rituximab (N = nnn)
0	Total (n)	nn
	1	nn (xx.x%)
	2	nn (xx.x%)
	3	nn (xx.x%)
	4	nn (xx.x%)
	Missing	nn (xx.x%)
1	Total (n)	nn
	1	nn (xx.x%)
	2	nn (xx.x%)
	3	nn (xx.x%)
	4	nn (xx.x%)
	Missing	nn (xx.x%)
...		


ID: LB004SP
 
Listing of Normal Ranges for Laboratory Tests
	
STREAM Template: None
 
Analysis Population: Safety Evaluable Population
 
Variables Displayed: Name of Lab test, Lab ranges Low-High under Lab Parameters (with unit), grouped by age and gender.
 
Numeric Precision and Formatting of Statistics: See mockup

---	---

Lab Test	Lower Lab Range				Upper Lab Range				Unit
	Age		Gender		Age		Gender		
	<12	>=12	Female	Male	<12	>=12	Female	Male	
<Lab Test>	xx	xx	xx	xx	xx	xx	xx	xx	xx
	xx	xx	xx	xx	xx	xx	xx	xx	xx
	xx	xx	xx	xx	xx	xx	xx	xx	xx
	xx	xx	xx	xx	xx	xx	xx	xx	xx
	xx	xx	xx	xx	xx	xx	xx	xx	xx

ID: LB004.1SP
 
Listing of lab abnormalities
	
STREAM Template: LBL02A
 
Analysis Population: Safety Evaluable Population
 
Numeric Precision and Formatting of Statistics: Add a column for "date of first drug administration" to LBL02A.

--	--

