- Hematology or complete blood count: hemoglobin, hematocrit, red blood cells and indices (mean corpuscular volume, mean cell hemoglobin, mean corpuscular hemoglobin concentration), white blood cells, absolute differential, and platelet counts
- Serum chemistry: AST/SGOT, ALT/SGPT, alkaline phosphatase, total protein, total bilirubin (direct and indirect will be performed if total bilirubin is greater than the ULN), urea, uric acid, creatinine, potassium, sodium, chloride, calcium, phosphate, and glycosylated hemoglobin (HbA_{1c}).
- Urinalysis: microscopic examination if abnormal and applicable
- Pregnancy test: A serum pregnancy test will be performed at screening for all females of childbearing potential
- Hepatitis serology: HBcAb, HBsAg, and hepatitis C antibody (HCV Ab) at screening only or if clinically indicated during the trial

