3. STATISTICAL METHODS OVERVIEW

As this is an open-label, single-arm study, with primary objectives regarding safety and PK there will be no formal statistical hypothesis testing.

The day of enrollment (Day 1) will be considered the day the patient receives their first infusion, or part thereof, of rituximab.

For binary endpoints the number and percentage of patients will be presented by visit. At key time points (Month 6, 12 and 18) two-sided 95% Confidence intervals (CIs) for the percentage of patients will be calculated.

For continuous endpoints, the n, mean, median, standard deviation (SD), minimum and maximum values will be presented by visit with two-sided 95% CIs for the mean presented for the data at key time-points (Months 6, 12 and 18), unless stated otherwise.

When we have 0 counts, please don't display 0.0%

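### The LB001SP differential list omits eosinophils, contrary to the table's stated scope, so out-of-range eosinophil counts would be missing from the laboratory abnormality tables

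*SAP*

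**What the plan says.** Protocol Section 4.5.3.5 sends a blood count to the central laboratory that includes "white blood cells, absolute differential, and platelet counts". It neither names the cell types of the differential nor excludes any. SAP Section 7.1 states that "Safety hematology and serum chemistry laboratory samples are taken during each planned study visit", and the schedules of assessments in both documents mark hematology in every visit column.

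For hematology and chemistry parameters, SAP Section 7.1 promises descriptive summaries and "The number of patients with values outside the normal upper and lower limit at each visit". No component is exempted. SAP Section 2.1.1 lists "Frequency of laboratory abnormalities" as a primary safety outcome, as does Protocol Section 3.4.1.1.

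SAP Section 7.4 specifies the tables. LB001SP (results and change from baseline) opens with "Single output file with separate page for each lab parameter as required by the protocol" and then gives the differential as "absolute differential [neutrophils, lymphocytes, monocytes, basophils], and platelet counts". LB004SP (abnormalities by visit and baseline status) and LB005SP (CTCAE shift table, hematology) both carry the instruction "See LB001SP for parameters to be included and the appropriate analysis visits".

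**The concern.** The bracketed list in LB001SP has four cell types, and eosinophils are not among them. The two tables that count abnormal values have no parameter list of their own and inherit this one. If the list is programmed as written, the omission passes from a descriptive table into the tables that deliver a primary safety outcome.

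At stake is the completeness of the laboratory safety reporting. SAP Section 7.1 leads a reader to expect, for every hematology parameter, the number of children outside the normal range at each visit. For eosinophils that number would not be tabulated, although the data would in all likelihood be in the database.

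**Working it through.** The plan gives no figure to reproduce here, so the check is a comparison of texts.

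**Step 1: is the differential restricted in the protocol?** No. Protocol Section 4.5.3.5 asks for the absolute differential without qualification.

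**Step 2: does LB001SP follow the protocol panel elsewhere?** Yes.

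| Panel item | Protocol 4.5.3.5 | LB001SP |
|---|---|---|
| Chemistry | 14 items | the same 14 items |
| Hemoglobin, hematocrit, red cells, three red-cell indices, white cells, platelets | all named | all named |
| Differential | unrestricted | neutrophils, lymphocytes, monocytes, basophils |

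The only narrowing is inside the SAP's own bracket. The bracket keeps basophils, so it does not look like a deliberate cut to the leading cell types. No reason for the omission is given.

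**Step 3: does LB001SP agree with itself?** No. Its opening sentence claims every parameter the protocol requires. If eosinophils belong to the protocol's differential, that sentence includes them and the bracket leaves them out.

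**Step 4: where does the list lead?**
- LB004SP, which gives low, normal and high counts by visit, refers back to LB001SP. The SAP uses the identifier LB004SP a second time for a listing of normal ranges; the abnormality table is meant here.
- LB005SP, which gives highest post-baseline CTCAE grade against baseline grade, also refers back to LB001SP.
- LB004.1SP, the listing of laboratory abnormalities, has no such reference and is not tied to the list.
- No visible output specification adds eosinophils back.

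**Step 5: extent.** LB001SP and LB004SP tabulate Baseline, Weeks 1 to 3, and Months 1, 2, 4, 6, 12 and 18, which is 1 + 3 + 6 = 10 visits. The differential has 4 named components now and would have 4 + 1 = 5 after the fix. As written, eosinophils are absent at all 10 visits from both tables, and from LB005SP so far as a grade would apply.

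**Step 6: what still captures an abnormal value?** The LB004.1SP listing does. So does the adverse event route: SAP Section 7.1 and Protocol Section 5.3.6 send clinically relevant or significant treatment-emergent abnormalities to the adverse event form. From there they enter the adverse event tables with patient counts. What is lost is the count of out-of-range values in general, including those that do not meet the clinical-significance criteria.

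**The case against.** Several objections have force.

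- **Measurement is inferred.** Neither document says that eosinophils are reported, and the central laboratory's panel is not described. The point rests on the usual meaning of an absolute differential. This stands as a limit, and the sponsor can settle it in one sentence.
- **The opening sentence of LB001SP may govern.** Together with SAP Section 7.1 it could be read as already requiring eosinophils, which would make the bracket merely incomplete. That is a fair reading, but it does not remove the problem. An explicit list is what is likely to be programmed, and here it contradicts the sentence above it.
- **A listing may be enough.** Protocol Section 6.6 allows safety parameters to be summarized or listed, and with about 25 children a count could be taken from LB004.1SP by hand. This meets the protocol. It does not meet the SAP's own promise of out-of-range counts by visit.
- **Nothing is tested.** The SAP states that "there will be no formal statistical hypothesis testing". No inference depends on this table.

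A reader might also infer that the omission hides a hypersensitivity signal, or matters because Protocol Appendix 6 links Churg-Strauss syndrome to eosinophilia. The documents do not support either inference. They draw no link between eosinophils and reactions to rituximab, and SAP Section 6 captures hypersensitivity directly through the definition of infusion-related reactions. Churg-Strauss syndrome is an entry exclusion, which gives no reason for tabulating eosinophils after treatment starts.

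**Conclusion.** The concern holds as a mismatch inside one output specification. The bracket in LB001SP disagrees with its own scope statement, with SAP Section 7.1 and with the protocol's unrestricted differential, and LB004SP and LB005SP inherit it. Out-of-range eosinophil values would not be tabulated by visit or grade, though the laboratory abnormality frequency is a primary outcome.

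The size is small. A reader might infer that abnormal eosinophil values go unreported altogether; they do not, because the LB004.1SP listing and the adverse event tables remain. A reader might also infer that the reported abnormality frequency is biased, for instance by 1/25 = 4% for each affected child. That does not follow. LB004SP counts are made per test and per visit, its percentages use the number of patients at that visit, and no composite abnormality rate is specified. A missing analyte changes no other reported percentage. The loss is completeness of the descriptive safety tables.

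The conclusion assumes that the central laboratory reports eosinophils within the differential, and that the tables would be programmed from the enumerated list.

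**What to change.** Add eosinophils to the bracketed differential list in LB001SP. They then carry through to LB004SP by the existing cross-reference, and to LB005SP where a CTCAE grade exists. If the central laboratory does not report them, or if the exclusion is intended, say so in one sentence in SAP Section 7.4.

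The cost is one word in the SAP and an extra page in the affected outputs. If the differential is reported in the usual way, the data are already collected; no sampling, visit or protocol change is needed.
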